10.2.2. Demographics and Medical History

Demographic information (eg, age, race, ethnicity, body weight, height, body mass index) and medical history (including treatment history) will be obtained for all patients.

10.2.3. Genotyping

10.2.3.1. DMD

A blood sample will be obtained to determine DMD genotype (or confirm if previously tested). Patients not previously genotyped may be consented and have genotype performed as part of the study. The blood sample for genotyping can be drawn at the Screening visit or any time prior to the Week 2 visit so that total blood volume taken for the Screening visit does not exceed recommendations (Section 17.1). Patients may start dosing based on historical genotyping results, provided that these results fulfill the required criteria described in Inclusion Criterion #2 (Section 8.2); however, all patients must undergo genetic testing to confirm the deletion mutation amenable to exon 51 skipping. Patients whose genotype is not confirmed to be amenable to exon 51 skipping will be withdrawn from the study.

10.2.3.2. LTBP4 and SPP-1

A blood sample will be obtained for latent transforming growth factor beta (TGF) binding protein 4 (LTBP4) and secreted phosphoprotein 1 (SPP-1) genotype for sensitivity analysis. The blood sample for single-nucleotide polymorphism analysis can be drawn at the Screening visit or any time during the dose-titration period, such that total blood volume taken at any given visit does not exceed recommendations (Section 17.1).

10.2.4. Other Assessments

Screening will also include clinical safety laboratory assessments, vital signs, physical examination, height/length and weight, a 12-lead ECG, an ECHO, assessment of previous and current medications/therapies, assessment of pre-treatment AEs,

10.3. Safety Assessments

10.3.1. Physical Examination

The Investigator or a medically qualified Subinvestigator will perform physical examinations at designated study visits, including examination of general appearance; head, ears, eyes, nose, and throat (HEENT); heart; lungs; chest; abdomen; skin; lymph nodes; musculoskeletal; and neurological systems.

10.3.2. Vital Signs

Vital signs (blood pressure, heart rate, respiration, and temperature) will be measured at the time points specified in Table 2 and Table 3. Refer to the Study Operations Manual for more details on the methods for obtaining vital signs.

For infusion visits, vital signs are to be collected within 60 minutes prior to infusion and within 5 ± 2 after the end of infusion, and at 30 ± 5 , and 60 minutes ± 10 after the end of the infusion. If the patient has not experienced an infusion reaction after the first 48 weeks of treatment, vital sign assessments may be limited to approximately 30 minutes prior to infusion and approximately 30 minutes after the end of the infusion. All assessments will be performed after patients have remained calm for 5 minutes. Pulse rate and respiratory rate should be measured over 1 minute.

10.3.3. Height/Length and Weight

Height/length and weight will be measured at the time points specified in Table 2 and Table 3 prior to study drug infusions, to determine the volume of study drug to be administered. Details about how weight measurements are obtained are provided in the Study Operations Manual. If a patient's weight or height/length varies by more than 10% from the prior visit, the patient should be re-weighed to confirm the result, and an explanation of the change should be documented.

10.3.4. Safety Monitoring, Additional Investigations and Stopping Rules

10.3.4.1. Safety Monitoring for Liver Chemistry Tests

Liver chemistry tests need to be monitored as specified in the Schedule of Events (Table 2). Initial abnormal liver chemistry test result(s) needs to be confirmed if:

• Gamma-glutamyl transferase (GGT) or glutamate dehydrogenase (GLDH) or Aspartate aminotransferase (AST) or Alanine aminotransferase (ALT) measurement is > 3 x the upper limit of normal (ULN) (or > 2 x Baseline value if the Baseline value was > ULN) at any time during the study.

Patients with confirmed liver chemistry test results (as above) need to have their liver chemistry tests (GGT, GLDH, ALT, AST, alkaline phosphatase (ALP), international normalized ratio (INR) and total bilirubin) retested two or three times weekly. Frequency of retesting can decrease to once a week or less if abnormalities stabilize or the trial drug has been discontinued and the subject is asymptomatic.

Additional Investigations:

Patients with confirmed abnormal liver chemistry test results (as above) are recommended to have the following evaluations performed:

- Obtaining a more detailed history of symptoms and prior or concurrent diseases.
- Obtaining a history of concomitant drug use (including nonprescription medications and herbal and dietary supplement preparations), alcohol use, recreational drug use, and special diets.
- Ruling out acute viral hepatitis types A, B, C, D, and E; autoimmune or alcoholic hepatitis; Non-Alcoholic SteatoHepatitis; hypoxic/ischemic hepatopathy; and biliary tract disease.
- Obtaining a history of exposure to environmental chemical agents.
- Additional liver evaluations, including gastroenterology/hepatology consultations, hepatic computed tomography (CT) or magnetic resonance imaging (MRI) scans, may be performed at the discretion of the Investigator, in consultation with the Sponsor Medical Monitor.

Stopping Rules for Liver Test Results:

In the event of laboratory results meeting the following criteria, and the event is without an alternative explanation as discussed with the Sponsor Medical Monitor, dosing of a patient with eteplirsen will be stopped permanently; values that are not confirmed due to failure to retest or missing lab values will be presumed confirmed:

- GGT or GLDH > 8 x ULN, which is confirmed
- GGT or GLDH > 5 x ULN, which is confirmed and persists for ≥ 2 weeks
- GGT or GLDH > 3 x ULN, which is confirmed **and** total bilirubin > 2 x ULN or INR > 1.5
- GGT or GLDH > 3 x ULN which is confirmed, and the new appearance (ie, onset coincides with the changes in hepatic enzymes) of fatigue, nausea, vomiting, right upper quadrant pain or tenderness, fever, rash, or eosinophilia (> 5%) felt by the Investigator to be potentially related to hepatic inflammation.

10.3.4.2. Safety Monitoring for Renal Function

Renal tests need to be monitored as specified in the Schedule of Events (Table 2). Patients with the following test results need to undergo repeat testing for confirmation of abnormal test results:

- Protein $\geq 2+$ (dipstick)
- Urine Protein to Creatinine Ratio (UPCR) ≥ 150mg/g
- Urine Albumin to Creatinine Ratio (UACR) ≥ 30mg/g
- Serum Creatinine ≥ 0.3 mg/dL above baseline

- Serum Creatinine > 1.5x ULN
- Estimated glomerular filtration rate (eGFR) \leq 60 ml/min/1.73m2
- Red blood cells (RBCs) > 1/hpf
- Elevated Cystatin C > ULN
- Elevated kidney injury molecule 1(KIM-1) > ULN

Additional Investigations:

24- hour urine collection needs to be undertaken to quantify any proteinuria and glomerular filtration rate (GFR) changes indicated by confirmed results as above. Additional evaluations including nephrology consultation, renal US/CT/MRI, renal biopsy, may be performed at the discretion of the Investigator in consultation with the Sponsor Medical Monitor.

Stopping Rules for Renal Test Results:

In the event of laboratory results meeting the following criteria, and the event is without an alternative explanation as discussed with the Sponsor Medical Monitor, dosing of a patient with eteplirsen will be stopped permanently:

- Quantitative total urine protein measurement of ≥ 1 g/24 hours
- Measured GFR (creatinine clearance) ≤ 45 mL/min/1.73m²
- Gross hematuria
- Any RBC Casts
- Persistent microscopic hematuria \geq 3 RBCs/hpf for 3 consecutive weeks

Safety Monitoring for Hypersensitivity

Patients will be monitored for occurrence of allergic reactions primarily via monitoring adverse events as specified in the Schedule of Events (Table 2). Patients will be instructed to promptly report any signs or symptoms of fever or constitutional symptoms that may arise during the study and the Investigator needs to closely evaluate all potential causes, including concomitant illness.

Additional Investigations:

Patients who experience significant or persistent constitutional symptoms need to be discussed with the Sponsor Medical Monitor to determine whether additional monitoring or laboratory tests are required. Additional evaluations including immunology consultation, tests for allergic reactions (absolute eosinophils, serum/plasma tryptase), may be performed at the discretion of the Investigator in consultation with the Sponsor Medical Monitor.

Stopping Rules for Hypersensitivity AEs:

In the event of a confirmed hypersensitivity AE meeting the following criteria, and the event is without an alternative explanation as discussed with the Sponsor Medical Monitor, dosing of a patient with eteplirsen will have their treatment permanently discontinued.

- Anaphylaxis, anaphylactoid reaction, or angioedema
- Any serious allergic reaction

Safety Monitoring for Platelet Count Results

The platelet count needs to be monitored as specified in the Schedule of Events (Table 2).

Patients who have a confirmed occurrence of platelets < 75,000/ mm³ need to have the following evaluations performed:

- Complete blood count (CBC) with reticulocytes
 - Peripheral blood smear
 - Coagulation panel (prothrombin time /INR, activated partial thromboplastin time)
 - High-sensitivity C-reactive protein

Additional Investigations:

Additional platelet evaluations for confirmed, unexplained significant platelet count reductions, including hematology consultation, fibrinogen, fibrinogen split products/D-dimer, von Willebrand factor, total immunoglobulins, complement levels, viral serologies, auto-antibody screen, antiplatelet antibodies and anti-PF4 assay, may be performed at the discretion of the Investigator in consultation with the Sponsor Medical Monitor.

Stopping Rules for Platelet Test Results:

In the event of laboratory results meeting the following criteria, and the event is without an alternative explanation as discussed with the Sponsor Medical Monitor, dosing of a patient with eteplirsen will be stopped permanently:

• Platelet count < 50,000/mm³

Safety Monitoring for Rhabdomyolysis

Rhabdomyolysis must be monitored by urine dipstick and adverse events as specified in the Schedule of Events (Table 2).

Patients who have confirmed heme+ dipstick urinalysis need to be evaluated for urine microscopy and the following AEs:

Rhabdomyolysis

- Acute onset or exacerbation of Myalgia
- Myoglobinuria
- Chromaturia (eg, tea-colored urine)

Additional Investigations:

In case of any of the adverse events above, subjects need to have evaluations of myoglobinuria, creatine kinase (CK), renal function (eg, serum cystatin C) and serum chemistry two or three times weekly until values reach usual/pre-event levels or stabilize.

In addition, investigators should obtain a more detailed history of symptoms, preceding activity and hydration status, concomitant drug use, and recent or concurrent infections. Additional evaluations, including rheumatology/immunology consultations and anti-muscle antibodies, may be performed at the discretion of the Investigator in consultation with the Sponsor Medical Monitor.

10.3.5. Clinical Safety Laboratory Evaluations

The following routine clinical safety laboratory tests will be collected at the time points specified in Table 2 and Table 3, will be analyzed by an accredited central laboratory selected by the Sponsor, and will be prepared according to the Laboratory Manual provided for the study:

Chemistry: Sodium, chloride, potassium, calcium, glucose, creatinine, blood urea

nitrogen (BUN), albumin, uric acid, total bilirubin, ALP, amylase, ALT, AST, GGT, GLDH, C-reactive protein (CRP), CK, and serum

cystatin C

Hematology: CBC with differential

Coagulation Screen: Prothrombin time, International Normalized Ratio, and activated

partial thromboplastin time

Routine Renal Monitoring

- Quantitative urinalysis: total protein to creatinine ratio (UPCR), urine albumin-to-creatinine ratio (UACR), kidney injury molecule 1 (KIM-1), and urinalysis (pH, specific gravity, protein, glucose, ketones, cytology, hemoglobin
- Renal function blood tests: creatinine, blood urea nitrogen, and cystatin C
- Urine dipstick testing

Persistent, unexplained abnormalities on routine renal blood test monitoring will result in additional renal function tests such as eGFR and 24 hour urine testing for protein.

Any value outside of the current reference ranges for the laboratory performing the test will be flagged on the laboratory results. The Investigator will determine whether abnormal assessment

results are clinically significant or not. Clinical significance is defined as any variation in assessment results that has medical relevance resulting in an alteration in medical care. If clinically significant deterioration from baseline levels is noted, the Investigator will continue to monitor the patient with additional assessments until:

- Values have reached normal range and/or baseline levels; or
- In the judgment of the Investigator together with the Sponsor's Medical Monitor, abnormal values are assessed to be not related to the administration of IP or other protocol-specific procedures, and additional assessments are not medically indicated.

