- Patients should receive eteplirsen once every 7 days starting on Study Week 1. A window of ±3 days from the scheduled dose is acceptable after the first infusion. Patients may not receive 2 separatedoses of eteplirsen within the same 60-hour period. The Medical Monitor should be contacted in the event of >2 consecutive missed doses.
- m. Renal function blood tests includecreatinine, blood urea nitrogen, and serum cystatin C.
- ^{n.} Quantitativeurine analysis includes KIM-1 and urinalysis (pH, specific gravity, protein, glucose, ketones, cytology, and hemoglobin).

Table 3: Schedule of Events: Week 49 through Week 96 and End-of-Study Follow-up

Study Period	Stable Dose Treatment Period									
Visit/Week	49	60	72	84	96/ET ^a	Safety F/Ub				
Clinical safety laboratory sample ^c		X	X	X	X	X				
Vital signs ^d		On weekly i	nfusion days		X	X				
Weight ^e		We	ekly		X	X				
Urine dipstick testing		We	ekly							
Renal function blood tests ¹	X	X	X	X	X					
Quantitative urine analysis ^m	X	X	X	X	X					
Physical examination (including height/length) ^f		X	X	X	X	X				
12-lead ECG ^{h,j}		X	X	X	X					
ECHO ^{h,j}		X	X	X	X					
Eteplirsen dosing ^k										
Concomitant medications			Continuous			X				
AE monitoring			Continuous			X				

Abbreviations: AE = adverse event;

ECHO = echocardiogram; ET = early termination; F/U = follow up;

; ECG= electrocardiogram; ; IV = intravenous;

- ^a Early termination assessments are thesame as Week 96 assessments.
- ^b A Safety Follow-up visit will occur approximately 4 weeks after the last infusion regardless of thepatient's duration in the study.
- ^c Clinical safety laboratory assessments (blood chemistry [including liver function], hematology [including platelets], and coa gulation) will be obtained every 12 weeks after Week 48. (See Section 10.3.5 for the list of tests to be completed.)
- d Vital signs include blood pressure, heart rate, respiration, and temperature. On infusion days, vital signs will be measured approximately 60 minutes prior to infusion and at 5 minutes(±2), 30 minutes (±5), and 60 minutes (±10) after the end of the infusion. If the patient has not experienced an infusion reaction after the first 48 weeks of treatment, vital signs may be limited to approximately 30 minutes prior to infusion and 30 minutes (±5) after theend of the infusion. All assessments will be performed after patients have remained calm for 5 minutes. Pulse rate and respiratory rate should be measured over 1 minute.

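### eGFR below 60 is a nephrotoxicity AESI and a repeat-test trigger, but no scheduled visit calls for eGFR and neither document gives an equation

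*Protocol*

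**What the plan says.** **Trigger.** Protocol 10.3.4.2 sends renal monitoring to Table 2 and introduces its list with "Patients with the following test results need to undergo repeat testing for confirmation of abnormal test results". One of the nine items is an eGFR at or below 60 mL/min/1.73 m².

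**AESI.** Protocol 11.3.9 names two nephrotoxicity criteria: proteinuria above 500 mg/24 hr and eGFR below 60. Both must be reported within 24 hours of awareness. SAP 6.8.2 repeats them.

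**Routine tests.** Protocol 10.3.5 opens with "The following routine clinical safety laboratory tests will be collected at the time points specified in Table 2 and Table 3". Its renal blood entry is "Renal function blood tests: creatinine, blood urea nitrogen, and cystatin C", which agrees with Table 2 footnote m and the matching Table 3 footnote. The chemistry panel lists creatinine and cystatin C but not eGFR.

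**When eGFR is done.** The same section then says: "Persistent, unexplained abnormalities on routine renal blood test monitoring will result in additional renal function tests such as eGFR". The sentence goes on to 24-hour urine protein.

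**Definition.** SAP 5.7 contains no derived eGFR variable. Neither document says whether eGFR rests on creatinine or cystatin C, or who calculates it.

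**The concern.** One section treats eGFR as a value that the site already holds and must act on. Another treats it as a later test, done once something else has stayed abnormal. A site that follows 10.3.5 as written has no eGFR to compare with 60 when the routine result arrives.

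The AESI is where this matters most. The 24-hour clock starts at awareness, and nobody becomes aware of a value that nobody was told to calculate. Sites that do calculate it may use different equations and so classify the same child differently. Decreased renal function is a named eteplirsen risk (Protocol 5.5), and the drug has not been studied before in this age group (Protocol 5.4). With about 12 children in two cohorts of about 6, one child misclassified moves an incidence by about 1/12 = 8 percentage points overall, or 1/6 = 17 points within a cohort.

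**Working it through.** This is a consistency check, so there is no planned figure to reproduce. The counts come from Tables 2 and 3.

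**1. Scheduled draws that could yield an eGFR**
- Renal blood tests, Table 2: Weeks 2 to 12 (11 visits) plus Weeks 16, 18, 20, 24, 28, 32, 36, 40, 44 and 48 (10 visits) = 21.
- Renal blood tests, Table 3: Weeks 49, 60, 72, 84 and 96 = 5. Total 21 + 5 = 26.
- Clinical safety laboratory samples also contain creatinine and cystatin C (10.3.5 chemistry). Two of them, Screening and Safety Follow-up, are not renal visits.
- Union for a child treated to Week 96: 26 + 2 = 28 draws. Draws at which the text asks for eGFR: 0.

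**2. Is the height available, if an equation needs it?** Height/length is taken at physical examinations: Screening, Weeks 1, 4, 8, 12, 16, 20, then four-weekly to Week 48, Weeks 60, 72, 84 and 96, and Safety Follow-up. Across the 28 draws, the latest scheduled height is oldest at Week 7 (taken at Week 4) and Week 11 (taken at Week 8): 3 weeks.

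**3. What else would fire?**

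| Trigger in 10.3.4.2 | Number |
|---|---|
| Urine: dipstick protein, UPCR, UACR, red cells, KIM-1 | 5 |
| Blood: creatinine rise of at least 0.3 mg/dL, creatinine above 1.5 × ULN, cystatin C above ULN | 3 |
| eGFR | 1 |
| Total | 9 |

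The eight others each call for a repeat on a single result, with no requirement of persistence. Confirmed results then require a 24-hour urine collection to quantify proteinuria and changes in GFR.

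**4. What does eGFR add?**
- To the repeat-test list, little. An eGFR from cystatin C alone is a function of an analyte that already has its own trigger. An eGFR from creatinine overlaps with two triggers, such as "Serum Creatinine > 1.5x ULN". The documents give no reference ranges, so how often eGFR would be at or below 60 with all eight others silent cannot be computed.
- To the AESI list, half of the nephrotoxicity criteria. None of the other eight triggers is itself an AESI criterion. The second criterion, proteinuria per 24 hours, also needs a collection that is not scheduled. So neither nephrotoxicity criterion is evaluated by instruction at any scheduled visit.

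**The case against.** The strongest reply has four parts.

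- **The wording does not forbid earlier calculation.** Section 10.3.5 says when eGFR must be done, and names it as an example. It is a derived value, so its absence from lists of collected tests is weak evidence, and the central laboratory may report it under the Laboratory Manual. This stands in part: an equation may exist outside these documents. But 10.3.5 calls eGFR additional, every routine list omits it, and an equation elsewhere would not settle the conflict over timing.
- **Children with a renal signal are followed up anyway.** This stands. A reader might infer that falling renal function would go untested; the other triggers and the 24-hour collection contradict that.
- **The signal reaches the analysis.** This also stands. SAP 6.8.6 summarises the highest creatinine and cystatin C, and Appendix Table 1 flags either above ULN. The AESI table is built from reported AEs and can be produced without eGFR. The gap lies in recognising the event.
- **No report is late if the clock starts at awareness.** Formally correct, but this describes the gap and does not close it.

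A reader might also put the delay at 11 to 12 weeks after Week 49, the spacing of scheduled renal draws there. The documents do not support a fixed figure. The term *persistent* is undefined, repeat tests may come sooner with no stated time limit, and dipsticks continue weekly.

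**Conclusion.** The inconsistency is real and worth correcting, but its safety effect is modest. eGFR is one of nine repeat-test triggers and one of two nephrotoxicity AESI criteria, and it is requested at none of 28 suitable draws. The main consequence is that an eGFR-defined AESI may be recognised late, inconsistently across sites, or not at all. The loss to repeat testing is small and cannot be quantified from the documents.

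It might be inferred that the renal stopping rules fail too. They do not: the filtration criterion there is measured creatinine clearance at or below 45 mL/min/1.73 m², and no stopping rule uses eGFR.

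The conclusion assumes that sites follow 10.3.5 as written and that no unseen manual instructs routine eGFR reporting. If the Laboratory Manual already does so with one equation, what remains is to align the protocol and SAP with it.

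**What to change.** 1. In Protocol 10.3.5, and in the renal blood test and clinical safety laboratory footnotes of Tables 2 and 3, state that eGFR is calculated at every draw that includes creatinine and cystatin C: Screening (which gives a baseline), the renal visits and Safety Follow-up. Use one prespecified paediatric equation at all sites, with the latest height/length if the equation needs it.
2. Remove eGFR from the tests done only after persistent abnormality; 24-hour urine stays there.
3. Define the same equation in SAP 5.7, so that values below 60 can be checked against reported AESIs.

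All trigger, AESI and stopping thresholds stay as they are.

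**Cost.** One sentence in 10.3.5, four footnotes and one SAP definition, with no extra scheduled blood, urine or height measurement. Some additional confirmatory blood draws, and possibly 24-hour urine collections in very young children, may follow; their number cannot be predicted from the documents. They must fit the Section 17.1 limits. If a repeat uses the full 2.0 mL chemistry volume, it takes 2.0/4.0 = 50% of the 24-hour allowance of a 5 kg child.

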10.3.5.1. Laboratory Assessments of Interest

The review of the DMC will include evaluation of laboratory assessments of interest, which include:

- Any ≥Grade 2 (moderate) or serious event without an alternative etiology that the Investigator deems is related to study drug
- Two consecutive drug-related serum creatinine levels $\ge 2 \times ULN$ without an alternative etiology.
- CK levels >50,000 U/L
- A confirmed, unexplained, increase in GGT or GLDH >3 × ULN and either an increase in bilirubin >2 × ULN or nascent prothrombin time >2 × ULN concurrently, without an alternative etiology

